1.4 Randomization To Intervention Or Control Arm

At the completion of baseline (see 2.3 for details), participants will be randomized to intervention or control arm. At each site, half of the participants will form the intervention group and the remaining participants will form the control group. The UCSF statistician will use a random number generator (<https://www.randomizer.org/>) to randomly pick half of the 60 ID numbers from one site and put them into one group. The 30 non-chosen numbers will form a second group, The statistician will then randomly decide which group will be assigned to the control group and which one to the intervention group. The process will be repeated for the other site.

This randomized set of ID numbers will be shared with the intervention team (tech team) at each site and they will assign the next available ID on the list, thereby randomizing the participant, at the time of completion of baseline. The tech team will prepare the TMB device according to the intervention arm allocated and give the participant the TMB device (see section 7.1.4 for details below). The assessment team will be blinded to the allocation.

SECTION 2: ASSESSMENT: BASELINE AND FOLLOW-UP

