2.1 Introduction

The assessments are performed by the trained assessment team. Following are the different data collection components:

- Screening and eligibility assessment (Section 1.3.3)
- Questionnaires: Baseline, 3 month, 6 month, 9 month and 12 month follow-up
- Phlebotomy at BL, 6 months and 12 months, hair at BL and 12 months
- Electronic adherence monitoring devices
- Field notes (Maintained by assessment coordinators with details of challenges faced in the field. This can be related to recruitment, assessment, ART centers or any other part of assessment process.)

The table below outlines the assessment schedule for baseline and follow-up assessments:

Assessment	Questionnaire	Phlebotomy	Hair collection
Baseline	X	X	X
3M Follow-up	X		
6M Follow-up	X	X	
9M Follow-up	X		
12M Follow-up	X	X	X

The baseline assessment will be conducted on the same day the participant was screened and signs the consent. The baseline assessment will not be considered complete, and the person will not be considered enrolled until s/he has completed the questionnaire, phlebotomy, and hair sample collection. (Interview procedure detailed in section 2.4)

At baseline, all the participants will be provided a card with their assigned ID number. They will be informed to identify themselves according to ID numbers provided to them when they are calling the office phone numbers

Follow up dates are determined based on the baseline interview date. The interview can take place during a window of 15 days before and four weeks after this date, but the aim is to get the interview done as close to the target date as possible. If the interview cannot be completed within four weeks post the target date, the participant is considered lost to follow-up for that wave.

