Laboratory assays for hair concentrations conducted at UCSF:

The hair samples are delivered to the UCSF Hair Analytical Laboratory where nevirapine (NVP) and Efavirenz (EVF) is extracted and analyzed with liquid chromatography/tandem mass spectrometry (LC/MS/MS) using validated methods approved by the Division of AIDS' Clinical Pharmacology and Quality Assurance Program.

- The proximal section of the thatch of hair (generally about 1-2cm, depending on duration of exposure to be assessed) is cut down and chopped to 1-2 mm length segments and 5 mg is weighed and processed.
- NVP and EFV are extracted with (methanol : trifluoacetic acid (9:1) for NVP) solution and internal standard in a 37°C shaking water bath overnight (>12 hours), followed by extraction with 3.00mL methyl *t* *ert*-butyl ether/ethyl acetate (1:1) under weak alkaline conditions and then analyzed by LC/MS/MS.
- The LC/MS/MS procedure separates NVP And EFV by utilizing a Micromass Quattro LC system equipped with a Hypersil BDS C18 column (4.6 x 100 mm, 5 μ m particle size), a mobile phase system consisting of acetonitrile : water : acetic acid (50 : 50 : 0.15) (v:v:v) with 4 mM ammonium acetate for NVP and acetonitrile/water (65:35) (v:v) for EFV and mass spectrometric detection with positive ionization for NVP and negative ionization for EFV by ESI (Electrospray Ionization) and mass scanning by MRM (Multiple Reaction Monitoring) analysis.
- Data processing will be performed using Analyst data acquisition software.
- The relative error (%) and precision (coefficients of variation) for spiked quality control hair samples at low, medium and high concentrations are all <15%.
- A detailed methods paper on using LC/MS/MS analysis for EFV on is available at DOI: 10.1002/rcm.3750

SECTION 7:: TEL-ME-BOX PROCEDURES

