Trial number: NCT03086655

Tel-Me-Box:

Testing a New, Real-time Strategies for Monitoring HIV Medication Adherence in India

Statistical analyses Plan:

This is a feasibility trial of automated reminders from an electronic pillbox (the Tel-Me-Box). Feasibility analyses will include tabulation of preference for the different kinds of reminder available. Further descriptive analyses will include calculation of enrollment and retention rates over the 12-month follow-up period.

To assess if tailored real-time adherence feedback via Tel-Me-Box shows potential to improve adherence, we will compare adherence from Tel-Me-Box (quarterly assessment for 12 months), as well as HIV viral loads, and hair ARV levels (both every 6 months) in the intervention (Tel-Me-Box with reminder) and control groups (Tel-Me-Box without a reminder). We will also compare self-reported adherence (assessed quarterly) between the 2 arms. Differences between the two groups in change in the outcomes over time will be assessed via the interaction between time and group in GEE linear or logistic regression models, for continuous and categorical versions of the outcome variables, respectively. Count variables will be analyzed via Poisson or negative binomial regression, depending on absence (Poisson) or presence (negative binomial) of overdispersion in the data distribution. Robust standard errors will be used in cases of deviation from normality in the linear regression models. *Note that these analyses are for illustration purposes only, as these were not the primary analyses this pilot study was powered for.*

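### Low-severity improvement: for continuous viral load and hair level, the SAP's time-by-group contrast is a difference in change, and adjusting for the baseline already collected is usually more precise

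*SAP*

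**What the plan says.** The SAP is one short section. Continuous outcomes go into GEE linear models, and "Differences between the two groups in change in the outcomes over time will be assessed via the interaction between time and group". No baseline covariate, equal-baseline constraint, time coding or working correlation is given. The outcomes include "HIV viral loads, and hair ARV levels (both every 6 months"). The section ends: "Note that these analyses are for illustration purposes only, as these were not the primary analyses this pilot study was powered for".

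On timing, Protocol 1.4 states: "At the completion of baseline (see 2.3 for details), participants will be randomized to intervention or control arm". It allocates within site: "At each site, half of the participants will form the intervention group and the remaining participants will form the control group". Protocol 2.1 adds that "the person will not be considered enrolled until s/he has completed the questionnaire, phlebotomy, and hair sample collection", and lists "Phlebotomy at BL, 6 months and 12 months, hair at BL and 12 months". The laboratory part of Protocol 6.4.2 sends hair to a laboratory "where nevirapine (NVP) and Efavirenz (EVF) is extracted and analyzed with liquid chromatography/tandem mass spectrometry"; no other drug assay is described.

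**The concern.** Because baseline comes before randomisation, the two arms have the same expected baseline. Any baseline difference seen between them is chance. A difference-in-change contrast subtracts the whole baseline value, which amounts to fixing the regression slope of follow-up on baseline at 1. If the true slope is below 1, that over-corrects and adds noise. If it is above 1, it under-corrects. Estimating the slope, or constraining the baseline means to be equal, removes this noise and leaves the target effect unchanged.

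Only precision is at stake. Aim 3 (Protocol 1.1) asks the pilot for a preliminary effect estimate, so the width of the interval is much of what it delivers.

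**Working it through.** **Inputs.** There are 60 participants per arm (Protocol 1.1 and 1.3.1); 2 sites × (30 + 30) = 120 agrees with Protocol 1.4. The documents give no SD, correlation, effect size or power for these outcomes, so there is no figure of the plan's own to reproduce. *Assumed:* correlation rho between baseline and follow-up of 0.3, 0.5 or 0.7; follow-up SD = 1 and baseline SD = k; one follow-up visit; complete pairs.

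**Step 1: what the interaction estimates.** In two simulated trials of 120 participants with visits at 0, 6 and 12 months, the GEE 12-month contrast equalled the raw difference in mean change (0.4707 in one, 0.0929 in the other). This held for categorical and for linear time, under independence and exchangeable correlation. It also held in the two-visit design that the protocol gives for hair. A correlated working structure alone therefore does not bring in the baseline adjustment.

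**Step 2: variances.** Each is multiplied by 2/n for the arm contrast.

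- Change: 1 + k² − 2k·rho
- Adjusted: 1 − rho²
- Difference: (k − rho)², which is never negative

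At k = 1 the ratio of adjusted to change is (1 + rho)/2. Large-sample saving in variance:

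| k | rho 0.3 | rho 0.5 | rho 0.7 |
|---|---|---|---|
| 0.5 | 4% | 0% | 7% |
| 0.75 | 18% | 8% | 0.5% |
| 1 | 35% | 25% | 15% |
| 1.25 | 50% | 43% | 37% |

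For example, at k = 0.5 and rho = 0.5, change gives 1 + 0.25 − 0.5 = 0.75 and adjusted gives 1 − 0.25 = 0.75.

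**Step 3: finite samples.** Estimating one slope multiplies the adjusted variance by (N − 3)/(N − 4): 117/116 = 1.009 at N = 120 and 57/56 = 1.018 at N = 60. The 95% half-width is 1.96·√(2V/n), in follow-up SDs, at k = 1:

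| Pairs per arm | Contrast | rho 0.3 | rho 0.5 | rho 0.7 |
|---|---|---|---|---|
| 60 | change | 0.42 | 0.36 | 0.28 |
| 60 | adjusted | 0.34 | 0.31 | 0.26 |
| 30 | change | 0.60 | 0.51 | 0.39 |
| 30 | adjusted | 0.49 | 0.44 | 0.36 |

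Sixty pairs is an upper bound, because blood can be refused (Protocol 5.1) and hair assays are described for two drugs only. In 4,000 simulated trials per rho at 60 per arm and k = 1, the variance ratios were 0.68, 0.76 and 0.86. Both estimators averaged about 0.50 for a true effect of 0.50.

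**Step 4: worst case.** At k = rho nothing is gained and only the slope cost remains: 0.9% at 60 pairs per arm and 1.8% at 30. If hair is analysed separately by drug with half on each, the cost is 57/56, or 1.8%, and 27/26, or 3.8%.

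**Step 5: hair drug mix.** Suppose the two drugs' log levels differ by 2 within-drug SDs, with half of the participants on each. The between-drug variance is then t = 0.5 × 0.5 × 2² = 1. Adjusting for one pooled raw level leaves (1 + t) − (rho + t)²/(1 + t), which is 1.155 at rho 0.3 against 1.4 for change. The saving is 17.5%, 12.5% and 7.5% at the three rho values. Standardising within drug restores 35%, 25% and 15%.

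**Step 6: viral load at the assay limit.** If half the values are at the limit at both visits, the savings are 38%, 29% and 18%. If 70% are at the limit at baseline and 50% at follow-up, they are about 19%, 10% and 2%. The rho values here are those before censoring.

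**Step 7: two follow-up visits.** One slope shared across visits can lose. With rho 0.9 at 6 months and 0.3 at 12 months, the shared slope is 0.6 and the 6-month variance is 1 + 0.36 − 2(0.6)(0.9) = 0.28, against 0.20 for change. With baseline-by-visit it is 1 − 0.81 = 0.19.

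**Step 8: the common-baseline GEE.** With one scale parameter and exchangeable correlation, its implied slope is k·rho/[(1 + k²)/2]. At k = 1 this matches covariate adjustment. At k = 0.5 and rho = 0.5 the slope is 0.25/0.625 = 0.4 and the variance is 1 + 0.16(0.25) − 2(0.4)(0.25) = 0.84, against 0.75 for change, so 12% worse. The equivalence therefore needs similar SDs or visit-specific variances.

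**The case against.** The strongest reply is that nothing depends on this. The SAP describes a feasibility trial, calls these comparisons illustrative, and ties no decision to the interval width. Choosing between two valid, unbiased estimators in such an analysis is optional. That stands, and it is why the point is low severity.

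Second, the SAP does not write the model. If equal baseline means were intended, the adjustment is largely there already. That also stands as a possibility, in which case one clarifying sentence is enough. It does not remove the point, because a time-by-group interaction normally carries a free group main effect.

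Third, the gain is unknown. Entry selects on poor self-reported adherence (Protocol 1.2), which may compress baseline hair levels and push k below 1, where the saving is small. The equal-SD figures should not be read as the expected ones.

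Fourth, a collected baseline is not always a valid one. Rejected blood is redrawn (Protocol 5.2.5) and mis-taped hair is recollected (Protocol 6.2), possibly after the device has been issued. A covariate model drops a missing baseline. This also affects the change score, so it does not favour the present plan, but it does bear on the choice of remedy.

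Fifth, restricting hair to participants on the same drug at both visits would select on regimen changes made after randomisation. That is right, and the fix avoids it.

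**Conclusion.** The point holds as a cheap, low-severity improvement for continuous log10 viral load and log hair level. In large samples the baseline-adjusted contrast is never less precise than the difference in change. The saving is 35% to 15% for rho 0.3 to 0.7 with equal SDs, and near zero when the baseline SD is about rho times the follow-up SD. All rho, k, drug-mix and assay-limit values are assumptions, and the SAP's model is assumed to have a free group main effect.

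A reader might infer three stronger things that the documents do not support:

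- **That the SAP's contrast is biased or wrong.** It is unbiased under randomisation.
- **That the trial gives up a known quarter or third of its precision.** No SD or correlation is given, so no single figure can be claimed.
- **That all of Aim 3 is affected.** Device adherence has no baseline, because the device is first handed out at the baseline session (Protocol 2.3.3). Suppression is a logistic outcome, for which adjustment changes the odds ratio being estimated. Of the three Aim 3 outcomes only hair level is covered; continuous viral load comes in through the SAP. Count models are not covered either.

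**What to change.** In the SAP, for log10 viral load and log hair level, specify one of two models:

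- **Covariate model.** Follow-up values on arm, visit, arm-by-visit, baseline and baseline-by-visit, with site as a factor because randomisation was within site. With a single follow-up visit the visit terms drop out.
- **Common-baseline model.** Baseline kept as an outcome row, arm means constrained equal at baseline, site as a factor, and a non-independence working correlation. Allow variances to differ by visit if the SDs are not similar (Step 8). This model also keeps participants whose baseline is missing, or was redrawn or recollected after randomisation; treat such late values as missing.

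For hair, standardise log level within drug (NVP or EFV) and keep every randomised participant with an assayable follow-up sample. Use same-drug pairs only as a sensitivity analysis, with counts by arm.

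The cost is SAP wording, a little more analysis work and a few extra parameters; no new data are needed. At worst (k = rho) one covariate slope costs about 1% more variance at 60 pairs per arm and 2% at 30. Separate analyses by drug, with half on each, cost about 2% and 4%.

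The SAP's six-monthly hair schedule and the protocol's baseline and 12-month schedule should be reconciled as a separate point. Baseline hair is collected under the protocol in any case, so this point does not depend on it.

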1.2 Eligibility

Potential participants must meet the following inclusion criteria to be considered:

- 18 years of age or older
- HIV-positive
- Currently on ART
- Speak one of the local languages
- Able and willing to participate in the study, provide informed consent, contact information, and express a willingness to return for follow-up visits as per the study schedule for the next 12 months.
- Adherence-challenged per self-report, i.e. report of <90% ART adherence or >2 ART treatment interruptions of at least 2 days in the past 3 months.
- Not used or participated in one of our previous studies, using AMD/TMB
- Live within 100 km of study site

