1.3 Recruitment, Screening and Enrollment

1.3.1 Enrollment Overview

A total of 120 participants will be enrolled with 60 in the intervention arm and 60 in the control arm from our Bangalore and Mysore sites.

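### Self-reported adherence is both entry criterion and outcome: with a cut-point at or above 90% and baseline as reference, the logistic time-by-group test may be inestimable or very imprecise

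*SAP*

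**What the plan says.** Protocol 1.2 admits people who are "Adherence-challenged per self-report, i.e. report of <90% ART adherence or >2 ART treatment interruptions of at least 2 days in the past 3 months". Protocol 2.1 adds: "The baseline assessment will be conducted on the same day the participant was screened and signs the consent". Randomisation follows completion of baseline (Protocol 1.4), and self-report is collected at baseline and at 3, 6, 9 and 12 months (Protocol 2.1).

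The SAP states: "We will also compare self-reported adherence (assessed quarterly) between the 2 arms". Its test for all outcomes is this: "Differences between the two groups in change in the outcomes over time will be assessed via the interaction between time and group", fitted in "GEE linear or logistic regression models, for continuous and categorical versions of the outcome variables, respectively". It does not give a cut-point or recall period for a categorical self-report outcome. It does not say whether time is linear or categorical, or how the baseline visit enters the model. It does not mention that this outcome is also the selection variable. It closes with: "Note that these analyses are for illustration purposes only, as these were not the primary analyses this pilot study was powered for".

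**The concern.** A test of change over time normally uses baseline as its starting point. Here everyone is selected on self-reported non-adherence, and the baseline questionnaire follows on the same day, so the answer has little time to move. If the categorical outcome is cut at or above the entry threshold, few participants, or none, can be adherent at baseline in either arm.

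A logistic interaction with baseline as reference subtracts the baseline log-odds in each arm. When those cells are nearly empty they supply most of the variance. Yet they were measured before randomisation and carry no information on the reminder. The likely result is a failed fit, or an interval so wide that it could be misread as no effect.

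**Working it through.** **The plan's own figures.** No power calculation is given, so there is none to reproduce. The counts agree: 2 sites × 60 = 120, and 30 per arm per site gives 60 per arm (Protocol 1.3.1 and 1.4).

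**Step 1: what the entry rule implies for baseline.** The criterion has two alternative routes.
- Below 90% adherence: non-adherent at any cut-point of 90% or more.
- More than 2 interruptions of at least 2 days: at least 3 × 2 = 6 missed days. Taking 3 months as about 91 days, adherence is at most 85/91 = 93.4%.

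For a consistent reporter on the same 3-month recall:
- At a 90% cut-point, the baseline adherent share is the share who enter only by the interruption route. The documents do not give it.
- At a 95% cut-point, the share is zero by both routes.
- At a lower cut-point such as 80%, or with a shorter recall, it need not be near zero.

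**Step 2: standard error at a single follow-up visit.** Inputs: n = 60 per arm (Protocol 1.3.1); follow-up adherent shares of 45% control and 65% intervention (assumed); visits treated as independent (assumed).

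The log odds ratio is ln(0.65/0.35) − ln(0.45/0.55) = 0.619 + 0.201 = 0.82.

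Each cell contributes 1/(n p(1−p)) to the variance:
- Follow-up cells: 1/(60 × 0.45 × 0.55) + 1/(60 × 0.65 × 0.35) = 0.0673 + 0.0733 = 0.1406. Without baseline, SE = √0.1406 = 0.37.
- Baseline cells at 3/60: 2 × 1/(60 × 0.05 × 0.95) = 0.7018. With baseline, SE = √(0.7018 + 0.1406) = 0.92.

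| Baseline adherent per arm | Interaction SE | Variance from baseline cells | Chance of an empty baseline cell in at least one arm |
|---|---|---|---|
| 0/60 | no finite estimate | – | certain |
| 1/60 | 1.47 | 94% | 60% |
| 3/60 | 0.92 | 83% | 9% |
| 6/60 | 0.71 | 72% | 0.4% |

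The last column is 1 − (1 − (1−p)^60)², taking the row's share as the true rate p. At 3/60 the 95% interval for the odds ratio extends by a factor of exp(1.96 × 0.92) ≈ 6 each way, against exp(1.96 × 0.37) ≈ 2 without baseline.

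**Step 3: simulated GEE over all visits.** Assumptions: 60 per arm, five visits, 45% vs 65% at every follow-up visit, correlated responses within person, no dropout, two-sided 5% level.
- Post-vs-baseline interaction: inestimable at a 0% baseline. Power is about 12% at a 5% baseline (12% to 17% across sets of runs), at most about 28% at 10%, and about 65% at 40%.
- Linear time: always estimable. Power is about 35% at a 0% baseline and 41% to 42% at a 30% to 40% baseline.
- Follow-up-only group effect: about 88% (86% to 92% across sets of runs).

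For post-vs-baseline coding the floor therefore does real damage. For linear time under a constant effect it costs only a few points. Most of the gap to 88% comes from testing a slope difference when the effect is a level difference.

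**The case against.** Three stronger readings are tempting, and the documents support none of them.

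*The baseline share is at or near zero.* The SAP names no cut-point or recall period. Screening uses its own form (Protocol 1.3.3), and the baseline questionnaire is not reproduced. The entry rule is an either/or rule, so at the trial's own 90% threshold some interruption-route entrants, reporting up to about 93%, count as adherent. The strict zero needs a 95% cut-point, which appears nowhere in the documents. This objection stands, so the point has to be conditional.

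*The test is undefined or has almost no power.* That holds only with baseline as reference. Linear time is an equally natural reading of the SAP, and it gives a defined test with about 5% size under the null, even at a 0% baseline. This stands too. A gradual effect may lose more with linear time: assuming a rise to 40% vs 60% by month 12, power was 18% at a 0% baseline and 56% at 30%. Those two cases also differ in their follow-up curves, so the gap cannot be put down to the floor alone.

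*The trial's adherence findings are at risk.* Only the categorical version of one added outcome is affected. The continuous self-report, device, viral load and hair outcomes do not have this empty-cell problem. Self-report is not among the outcomes named in Protocol 1.1, and the SAP calls these comparisons illustrative. This limits the severity.

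A further fair objection is that a constant effect from month 3 flatters an averaged follow-up contrast. It does, and the fix allows for it. What remains is that the SAP leaves the choice open, one permitted choice may fail, and a better randomised contrast is available from the same data.

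**Conclusion.** The concern holds conditionally. Entry on self-reported non-adherence, a same-day baseline and a time-by-group test are all in the documents, and the SAP does not say how they fit together. If the categorical outcome is cut at or above 90% on a similar recall, and baseline is the reference, the logistic interaction is inestimable at zero events and very imprecise near zero: SE 0.92 against 0.37 at 3/60, and about 12% power against about 88% at a 5% baseline. If time is linear, the test works but has only about 35% power in the same scenario, mainly because of the choice of test.

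The follow-up shares, baseline shares, cut-points, correlation and absence of dropout are assumptions; the documents give none of them. Severity is minor to moderate.

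**What to change.** For categorical self-reported adherence, the SAP should:
- State the cut-point and the recall period.
- Fit the logistic GEE to the 3, 6, 9 and 12 month values only, with visit and a group main effect, adjusted for baseline self-report in the form in which the questionnaire collects it.
- Report the odds ratio and the risk difference with 95% confidence intervals.
- Show baseline descriptively.
- Also show the arm difference at each visit, because the averaged contrast is less sensitive to an effect that emerges only late.

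Because allocation is randomised, comparing follow-up levels between arms is valid without subtracting baseline. The cost is a sentence or two in the SAP, with no new data and no change to visits.

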Trial number: NCT03086655

Tel-Me-Box:

Testing a New, Real-time Strategies for Monitoring HIV Medication Adherence in India

PROTOCOL

July 2, 2021

Table of Contents

SECTION 1: OVERVIEW.....	1
1.1 Aim 3	1
1.2 Eligibility.....	1
1.3 Recruitment, Screening and Enrollment	1
1.4 Randomization To Intervention Or Control Arm	3
SECTION 2: ASSESSMENT: BASELINE AND FOLLOW-UP.....	5
2.1 Introduction.....	5
2.2. Pre-Interview Procedures for All Waves.....	5
2.3. Baseline Interview Procedures:	6
2.4. Interview Procedures for 3m, 6m, 9m and 12m	8
SECTION 3: FOLLOW-UP, TRACKING, AND WITHDRAWAL	9
3.1. Identifying and Scheduling Participants for Follow-Up.....	9
3.2. Procedures for Making Follow-Up Calls	9
3.3. Home and Workplace Tracking and Assessment Visits:.....	11
3.4 Participant Withdrawal, Loss to Follow Up or Death	13
SECTION 4: DATA MANAGEMENT.....	16
4.1 Data Entry Procedures	16
4.2 Data Entry Verification	17
4.3 Data Upload Procedure and UCSF Review:.....	17
4.4. Data Storage / Maintaining Confidentiality	18
4.5. Data Backups.....	18
4.6 Data from TMB (Devices)	18
4.7 Data for Phlebotomy Lab Samples from RLS.....	18
SECTION 5: PHLEBOTOMY AND LAB PROCEDURES.....	20
5.1 Overview	20
5.2 Procedures	20
SECTION 6: HAIR COLLECTION AND LAB PROCEDURES	25
6.1 Hair Collection and Storage Tasks.....	25
6.2 Hair Collection Quality Control Procedures.....	25
6.3 Data	25
6.4 Hair Sampling: Schedule, Supplies, and Storage	25
SECTION 7:: TEL-ME-BOX PROCEDURES	33
7.1 TMB Procedures	33

7.2. TROUBLESHOOTING PARTICIPANTS' TMB BOX PROBLEMS.....	35
7.3 Device Return for Withdrawn Participants	38
APPENDIX A: TMB TRACKING FORM.....	39

SECTION 1: OVERVIEW

1.1 Aim 3

To perform a pilot RCT to estimate the effect of real-time adherence feedback delivered wirelessly through the Tel-Me-Box on hair ARV concentrations, device-monitored adherence and viral load suppression in adherence-challenged patients. Among adherence challenged-patients at SJRI without virologic resistance, this pilot will produce a preliminary estimate of the effect of real-time, wireless adherence feedback delivered in a tailored fashion via Tel-Me-Box on hair ARV concentrations, device-monitored adherence and virologic suppression compared to patients (60 in each arm) using Tel-Me-Box without real-time feedback.

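### The SAP ties robust standard errors to non-normality in the linear models, which is the wrong trigger for GEE and leaves the logistic models with no stated standard-error method.

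*SAP*

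**What the plan says.** The SAP compares the arms on change over time "via the interaction between time and group in GEE linear or logistic regression models, for continuous and categorical versions of the outcome variables". It adds that "Count variables will be analyzed via Poisson or negative binomial regression", with the choice between the two depending on overdispersion. The one sentence on standard errors is "Robust standard errors will be used in cases of deviation from normality in the linear regression models". Neither the SAP nor the protocol names a working correlation, a software package, or a standard-error method for the logistic or count models. Neither says whether time enters as a linear or a categorical term.

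Protocol section 1.1 states the purpose: "this pilot will produce a preliminary estimate of the effect of real-time, wireless adherence feedback", and it names virologic suppression among the outcomes. The SAP qualifies the comparisons by saying that "these analyses are for illustration purposes only, as these were not the primary analyses this pilot study was powered for".

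On the schedule, protocol section 2.1 has "Phlebotomy at BL, 6 months and 12 months, hair at BL and 12 months", with questionnaires at baseline and at 3, 6, 9 and 12 months. The SAP describes "HIV viral loads, and hair ARV levels (both every 6 months", which does not match the protocol for hair. The protocol schedule is used below.

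**The concern.** Model-based GEE standard errors are valid only if the assumed variance and within-person correlation are right. Sandwich errors remain valid in large samples when they are wrong. Non-normality is at best a loose proxy for a wrong variance and carries no information about correlation. For a binary outcome a normality check has no meaning.

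The rule therefore leaves two gaps:

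- The logistic models fall outside the trigger, so the analyst has no instruction for viral suppression or for a dichotomised adherence measure. The same holds for any count outcome measured repeatedly.
- A linear outcome that passes a normality check would, by implication, get model-based errors, even though passing says nothing about whether the working correlation is right.

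At stake is the stated uncertainty around the preliminary effect estimates. With complete data and a correct mean model, the choice of standard error does not bias the estimates themselves.

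**Working it through.** The documents give no significance level, correlation, prevalence or variance, so there is no planned figure to reproduce.

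**Inputs from the documents.** 60 per arm (protocol 1.1 and 1.3.1). Viral load at 0, 6 and 12 months; hair at 0 and 12; self-report at 0, 3, 6, 9 and 12 (protocol 2.1). Device adherence at 3, 6, 9 and 12 months, since the device is issued at baseline (protocol 2.3.3). The target is the time-by-group interaction (SAP).

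**Assumptions.** Complete data, no true effect, linear time, a 95% interval, and true correlation ρ^(months apart/3) with ρ from 0.5 to 0.9. For binary outcomes this correlation applies on the latent scale, with prevalence 50 to 85%.

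**Formulas.** Let W be the working and C the true covariance, A = ΣX′W⁻¹X and B = ΣX′W⁻¹CW⁻¹X. The model-based variance is A⁻¹ and the true (sandwich) variance is A⁻¹BA⁻¹. Let k be the ratio of model-based to true SE for the interaction. Then the miss rate is 2[1 − Φ(1.96k)].

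**Step 1: does non-normality matter?** Linear GEE with five waves, 60 per arm, 5,000 simulated trials per cell, model-based errors:

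| True correlation / working correlation | Normal errors | Skewed errors |
|---|---|---|
| AR(1) 0.8 / exchangeable | 18.5% | 18.2% |
| Exchangeable 0.5 / independence | 0.4% | 0.6% |
| Exchangeable 0.5 / exchangeable (correct) | 4.8% | 5.3% |

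The error distribution hardly changes the miss rate; the working correlation changes it a great deal.

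**Step 2: logistic models.** Simulation with n = 120; ρ = 0.5, 0.6, 0.7, 0.8, 0.9; prevalence 50, 70, 85%; at least 4,000 runs per scenario; Monte Carlo SE 0.1 to 0.6 points. Miss rates with model-based errors:

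| Outcome | Exchangeable | Independence |
|---|---|---|
| Viral suppression, 3 waves | 5.4–7.8% | 0.8–4.7% |
| Device adherence, dichotomised, 4 waves | 7.8–11.5% | 0.7–5.6% |
| Self-report, dichotomised, 5 waves | 9.2–14.2% | 1.4–7.0% |

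With robust errors the range is 4.6–6.5%. A large-sample calculation for three waves at 60% prevalence and ρ = 0.8 agrees: k = 0.92, miss rate 7.2%, under an exchangeable working correlation.

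**Step 3: linear models with two or three waves.** Here the slope contrast depends only on the 12-month minus baseline difference. With r₁₂ the 12-month correlation and a the mean pairwise correlation, k² = (1 − a)/(1 − r₁₂) under exchangeable and 1/(1 − r₁₂) under independence.

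- Three waves, exchangeable, ρ = 0.5: r₆ = 0.25, r₁₂ = 0.0625, a = (2 × 0.25 + 0.0625)/3 = 0.1875, k = √(0.8125/0.9375) = 0.931, miss rate 6.8%.
- Three waves, exchangeable, ρ = 0.9: r₆ = 0.81, r₁₂ = 0.6561, a = 0.7587, k = √(0.2413/0.3439) = 0.838, miss rate 10.1%. Intervals are thus 7 to 16% too narrow.
- Two waves (hair), exchangeable: a = r₁₂, so k = 1 and the miss rate is 5.0%.
- Two waves (hair), independence: k = 1/√(1 − 0.0625) = 1.033 to 1/√(1 − 0.6561) = 1.705. Intervals are 3 to 71% too wide, with miss rates of 4.3% down to 0.1%.

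Robust errors give 5.1–5.9% in the linear simulations.

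**Step 4: sensitivity.** If 30% of the variance is visit-specific noise, the three-wave exchangeable range falls to 6.2–7.1% for linear models. For logistic models it falls to 5.1–6.1%, against 4.6–5.8% with robust errors. With categorical time, linear models with two or three waves give 5.0–5.7% under exchangeable. With a correct working correlation the rate is 5.0%.

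**The case against.** The strongest reply is that the SAP says when robust errors are required and does not say that model-based errors apply elsewhere. A reader might infer that the plan bars robust errors in the logistic models. The text does not support that: it is silent there, and some GEE software may report robust errors by default. This part of the reply stands. But the SAP names no software, and a plan should not rest on an unstated default.

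The linear gap is also narrower than it looks. Continuous adherence is bounded and probably non-normal, so the SAP's own rule would probably give it robust errors. A reader might quote linear miss rates of 11.3–16.0% (four waves) or 13.6–20.8% (five waves) for it; those arise only if it is judged normal. The same applies to log viral load. If 50 to 85% of participants are suppressed and their values sit near an assay floor (an assumption), normality would fail: a normal variable censored at 50, 70 or 85% with n = 120 was rejected by a Shapiro test in all 500 runs at each level. The three-wave linear figures therefore probably describe a case that would not arise. Hair at two waves is harmed only under independence. If hair were measured every 6 months, as the SAP has it, the three-wave linear figures would apply to hair if it were judged normal.

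Two further limits stand. The main ranges rest on pure AR(1) correlation and linear time, which favour a visible effect. For three-wave viral suppression the model-based and robust ranges overlap. The dichotomised-adherence figures also need a cut-off that the SAP does not define, and no count outcome is named or said to be repeated.

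**Conclusion.** The point holds, with modest impact. The written trigger is wrong for GEE whatever the correlation turns out to be, and the logistic models have no stated method. Under the AR(1), linear-time and exchangeable assumptions, model-based intervals would miss about 5 to 8% of the time for viral suppression and about 8 to 14% for dichotomised adherence, against about 5 to 6.5% with robust errors. Under an independence working correlation the error mostly runs the other way, towards intervals that are too wide.

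These are illustrative ranges, not predictions for this trial. The harm arises only if model-based errors are used together with a wrong working correlation. The documents do not support reading this as a biased effect estimate or as a threat to the trial's conclusions: the comparisons are labelled illustrative, no significance level is set, and the feasibility results are tabulations and rates. What can be misstated is how much weight the preliminary estimates bear.

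**What to change.** Replace the SAP sentence on standard errors with wording such as:

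> All GEE models, linear and logistic, and any model for a repeated count outcome will report robust (sandwich) standard errors, whatever the outcome distribution.

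As a secondary clarification, name the working correlation for each outcome and state whether time is linear or categorical.

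The cost is one replaced sentence, one added sentence and a software option. Data collection does not change. With about 120 participants, robust errors stayed close to nominal in the scenarios above.
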